20.0 DATA SAFETY MANAGEMENT AND PROCEDURES

20.1 Design and Development

This protocol will utilize a centralized Data and Statistics Center (DSC). The DSC will be responsible for development of the electronic case report forms (eCRFs), development and validation of the clinical study database, ensuring data integrity, and training site and participating node staff on applicable data management procedures. AdvantageEDC, a web-based distributed data entry system, will be implemented. This system will be developed to ensure that guidelines and regulations surrounding the use of computerized systems used in clinical trials are upheld. The remainder of this section provides an overview of the data management plan associated with this protocol.

20.2 Site Responsibilities

The data management responsibilities of each individual CTP will be specified by the DSC and outlined in the AdvantageEDC User's Guide.

20.3 Data Center Responsibilities

The DSC will 1) develop a data management plan and will conduct data management activities in accordance with that plan, 2) provide final guided source documents and eCRFs for the collection of all data required by the study, 3) develop data dictionaries for each eCRF that will comprehensively define each data element, 4) conduct ongoing data monitoring activities on study data from all participating CTPs, 5) monitor any preliminary analysis data cleaning activities as needed, and 6) rigorously monitor final study data cleaning.

20.4 Data Collection

Data will be collected at the study sites either on source documents, which will be entered at the site into eCRFs, or through direct electronic data capture. The eCRFs will be supplied by the DSC. eCRFs are to be completed on an ongoing basis during the study. The medical chart and the source documents are the source of verification of data. Paper CRFs and eCRFs should be completed according to the CRF instruction manual and relevant instructions in the study operations manual. The investigator is responsible for maintaining accurate, complete and up-to-date records, and for ensuring the completion of the eCRFs for each research participant.

20.5 Data Acquisition and Entry

Completed forms and electronic data will be entered into the AdvantageEDC system in accordance with the AdvantageEDC User's Guide. Only authorized individuals shall have access to eCRFs.

20.6 Data Editing

Completed data will be entered into AdvantageEDC. If incomplete or inaccurate data are found, a query will be generated to the sites for a response. Site staff will resolve data inconsistencies and errors and enter all corrections and changes into AdvantageEDC.

20.7 Data Lock and Transfer

Data will be transmitted by the DSC to the NIDA central data repository as requested by NIDA. The DSC will conduct final data quality assurance checks and “lock” the study database from further modification. The final analysis dataset will be returned to NIDA, as requested, for storage and archive.

20.8 Data Training

The training plan for CTP staff includes provisions for training on assessments, eCRF completion guidelines, data management procedures, and the use of AdvantageEDC.

20.9 Data QA

To address the issue of data entry quality, the DSC will follow a standard data monitoring plan. An acceptable quality level prior to study lock or closeout will be established as a part of the data management plan. Data quality summaries will be made available during the course of the protocol.

22.0 APPENDIX A

ADVERSE EVENT REPORTING DEFINITIONS AND PROCEDURES

Each participating site's principal investigator is responsible for study oversight, including ensuring human research subject protection by designating appropriately qualified and trained study personnel to assess, report, and monitor adverse events.

22.1 Definition of Adverse Events and Serious Adverse Events:

An **Adverse Event** (AE) is any untoward medical occurrence in humans, whether or not considered study drug/intervention related which occurs during the conduct of a clinical trial. Any change from baseline in clinical status or any findings from ECGs, lab results, x-rays, physical examinations, etc., that are considered clinically significant by the study medical clinician are considered AEs.

Suspected adverse reaction is any adverse event for which there is a reasonable possibility that the study drug/intervention caused the adverse event. A reasonable possibility implies that there is evidence that the study drug/intervention caused the event.

Adverse reaction is any adverse event caused by the study drug/intervention.

An **adverse event, suspected adverse reaction, or adverse reaction** is considered "**serious**" (i.e., a serious adverse event, serious suspected adverse reaction or serious adverse reaction) if, in the view of either the study medical clinician or sponsor, it:

- 1) Results in death: A death occurring during the study or which comes to the attention of the study staff during the protocol-defined follow-up period, whether or not considered caused by the study drug/intervention, must be reported.
- 2) Is life-threatening: Life-threatening means that the study participant was, in the opinion of the medical clinician or sponsor, at immediate risk of death from the reaction as it occurred and required immediate intervention.
- 3) Requires inpatient hospitalization or prolongation of existing hospitalization.
- 4) Results in persistent or significant incapacity or substantial disruption of the ability to conduct normal life functions. Is a congenital abnormality or birth defect.
- 5) Important medical event that may not result in one of the above outcomes, but may jeopardize the health of the study participant or require medical or surgical intervention to prevent one of the outcomes listed in the above definition of serious event.

22.1.1 Definition of Expectedness

Any adverse event is considered "unexpected" if it is not listed in the investigator brochure or the package insert or is not listed at the specificity or severity that has been observed. If neither is available then the protocol and consent are used to determine an unexpected adverse event.

22.2 Pregnancy

Any pregnancies that occur while a participant is enrolled in the study will be captured on a pregnancy CRF and not separately reported as an AE or SAE. Women who become pregnant during the active treatment period will be discontinued from further medication administration, referred for medical care, and the pregnancy followed until an outcome is known.

22.3 Medical and Psychiatric History

A thorough medical and psychiatric history during the screening phase should record any chronic, acute, or intermittent preexisting or current illnesses, diseases, symptoms, or laboratory signs of the participant, to avoid reporting pre-existing conditions as new AEs and to assist in the assessment of worsening in intensity or severity of these conditions that would indicate an AE. Stable chronic conditions, such as arthritis, which are present prior to clinical trial entry and do not worsen are not considered AEs.

22.4 Site's Role in Eliciting and Reporting Adverse Events

Appropriately qualified and trained study staff will elicit participant reporting of AEs and SAEs at each study visit designated to collect AEs. Adverse events (medical and/or psychiatric) assessment will initiate with participant consent and follow-up will continue through 30 days post last study visit. Study staff will obtain as much information as possible about the reported AE/SAE to complete the AE/SAE forms and will consult as warranted.

Standard reporting, within 7 days of the site becoming aware of the event, is required for reportable AEs. Expedited reporting (within 24 hours of their occurrence and/or site's knowledge of the event) is required for reportable SAEs (including death and life-threatening events). Local sites are responsible for reporting SAEs to their IRB, per their IRB's guidelines.

Site staff is required to enter reportable AEs and SAEs in the AdvantageEDC system. The AE form is used to capture reportable AEs (as defined in the protocol). Additional information may need to be gathered to evaluate serious adverse events and to complete the appropriate CRFs and the summary. This process may include obtaining hospital discharge reports, medical records, autopsy records or any other type records or information necessary to provide a complete and clear picture of the serious event and events preceding and following the event. If the SAE is not resolved or stable at the time of the initial report or if new information becomes available after the initial report, follow-up information must be submitted as soon as possible.

Reportable adverse events will be followed until resolution, stabilization or study end. Any serious adverse reactions will be followed until resolution or stabilization even beyond the end of the study.

22.5 Site's Role in Assessing Severity and Causality of Adverse Events

Appropriately qualified and trained medical personnel will conduct an initial assessment of seriousness, severity, and causality when eliciting participant reporting of adverse events. A study medical clinician will review reportable AEs for seriousness, severity, and causality at least on a weekly basis.

22.6 Guidelines for Assessing Severity

The severity of an adverse event refers to the intensity of the event.

Grade 1	Mild	Transient or mild discomfort (< 48 hours), no or minimal medical intervention/therapy required, hospitalization not necessary (non- prescription or single-use prescription therapy may be employed to relieve symptoms, e.g., aspirin for simple headache, acetaminophen for post-surgical pain).
Grade 2	Moderate	Mild to moderate limitation in activity some assistance may be needed; no or minimal intervention/therapy required, hospitalization possible.
Grade 3	Severe	Marked limitation in activity, some assistance usually required; medical intervention/ therapy required hospitalization possible.

22.6.1 Guidelines for Determining Causality

The study medical clinician will use the following question when assessing causality of an adverse event to study drug/intervention where an affirmative answer designates the event as a suspected adverse reaction: Is there a reasonable possibility that the study drug/intervention caused the event?

22.6.2 Site's Role in Monitoring Adverse Events

Local quality assurance monitors (Node QA staff) will visit study sites and review respective study data on a regular basis and will promptly advise sites to report any previously unreported safety issues and ensure that the reportable safety-related events are being followed to resolution and reported appropriately. Staff education, re-training or appropriate corrective action plan will be implemented at the participating site when unreported or unidentified reportable AEs or serious events are discovered, to ensure future identification and timely reporting by the site.

22.6.3 Sponsor's Role in Safety Management Procedures of AEs/SAEs

A NIDA-assigned Medical Monitor is responsible for reviewing all serious adverse event reports. All reported SAEs will generate an e-mail notification to the Medical Monitor, Lead Investigator, and designees. All SAEs will be reviewed by the Medical Monitor in AdvantageEDC and, if needed, additional information will be requested. The medical monitor will also report events to the sponsor and the Data and Safety Monitoring Board (DSMB). The DSMB will receive summary reports of all adverse events annually, at a minimum. The DSMB or the NIDA assigned Medical Monitor may also request additional and updated information. Details regarding specific adverse events, their treatment and resolution, will be summarized by the medical monitor in writing for review by the sponsor and DSMB. Subsequent review by the Medical Monitor, DSMB, FDA and ethics review committee or IRB, the sponsor, or relevant local regulatory authorities may also suspend further trial treatment at a site. The study sponsor, DSMB and FDA retain the authority to suspend additional enrollment and treatments for the entire study as applicable.

22.7 Regulatory Reporting for an IND study

Not applicable as this study is not being conducted under an IND application.

[figure not shown]
22.8 Reporting to the Data and Safety Monitoring Board

The DSMB will receive a listing of AEs and summary reports of all SAEs at a frequency requested by the DSMB, but at least annually. Furthermore, the DSMB will be informed of expedited reports of SAEs.

22.9 Participant Withdrawal

The study medical clinician must apply his/her clinical judgment to determine whether or not an adverse event is of sufficient severity to require that the participant is withdrawn from further study medication administration. Extended-release naltrexone will be discontinued in participants with evidence of clinically significant deterioration in hepatic function and/or acute hepatitis, as assessed by the study clinician. The study medical clinician should consult with the site principal investigator, the lead investigator and/or Medical Monitor as needed. If necessary, a study medical clinician may suspend any trial treatments and institute the necessary medical therapy to protect a participant from any immediate danger. A participant may also voluntarily withdraw from treatment due to what he/she perceives as an intolerable adverse event or for any other reason. If voluntary withdrawal is requested, the participant will be asked to complete an end-of-medication visit to assure safety and to document end-of-medication outcomes and will be given recommendations for medical care and/or referrals to treatment, as necessary.

22.10 Adverse Event Reporting Chart

23.0 APPENDIX B

DATA SAFETY AND MONITORING PLAN (DSMP)

Brief Study Overview

The primary goal of the CTN-0055 study is to compare HIV viral suppression (HIV-1 RNA < 200 copies / ml at 6 months) among study participants randomized to XR-NTX vs those randomized to office-based BUP/NX. Secondary aims are to compare the effectiveness of XR-NTX vs BUP/NX in 1) HIV outcomes 2) engagement in HIV care 3) change in substance use, 4) change in HIV risk behaviors, 5) change in health related quality of life, and 6) participant safety. Details for the definitions and reporting of safety events are found in the protocol (Appendix A).

23.1 Oversight of Clinical Responsibilities

23.1.1 Site Principal Investigator

Each participating site's PI is responsible for study oversight, including ensuring human research subject protection by designating appropriately qualified, trained research staff and medical clinicians to assess, report, and monitor adverse events.

Regarding safety and in accordance with FDA reporting requirements, all Adverse Events (AEs) occurring during the course of the clinical trial will be collected, documented, and reported by the investigator or sub-investigators according to the Protocol. The assessment of Adverse Events (medical and/or psychiatric) will commence at the time of participant consent and will continue through 30 days post last active treatment visit.

The occurrence of AEs and Serious Adverse Events (SAEs) will be assessed at each clinic visit during the study. Serious adverse events will be followed until resolved or considered stable, with reporting to the CCC Safety Monitor/Medical Monitor through the follow-up period.

Standard reporting, within 7 days of the site becoming aware of the event, is required for reportable AEs. Expedited reporting (within 24 hours of their occurrence and/or site's knowledge of the event) is required for reportable SAEs (including death and life-threatening events).

23.1.2 Medical Monitor/Safety Monitor

The NIDA Clinical Coordinating Center (CCC) Safety Monitor/Medical Monitor is responsible for reviewing all adverse events and serious adverse events reported. All SAEs will be reviewed at the time they are reported in the EDC. The Medical Monitor will also indicate concurrence or not with the details of the report provided by the site PI. Where further information is needed the Safety monitor/Medical monitor will discuss the event with the site. Reviews of SAEs will be conducted in AdvantageEDC data system and will be a part of the safety database. All AEs are reviewed on a weekly basis to observe trends or unusual events.

The CCC Safety Monitor/Medical Monitor will in turn report events to the sponsor and regulatory authorities if the event meets the definition of an expedited event. All SAEs that meet expedited reporting based on federal regulations will be reported to the FDA in writing within 15 calendar days of notification of the CCC. If the SAE meets the criteria for death or immediately life-threatening, the CCC will notify the FDA electronically, by phone or by fax as soon as possible but no later than 7 calendar days of notification of the CCC, with a follow-up written report within 15 calendar days of notification of the CCC. The CCC will prepare an expedited report (MedWatch Form 3500A or similar) for the FDA and copies will be distributed to all site investigators. Reports will be generated and presented for Data Safety Monitoring Board (DSMB) meetings.

23.1.3 Data and Safety Monitoring Board (DSMB)

The NIDA CTN DSMB affiliated with this trial will be responsible for conducting periodic reviews of accumulating safety, trial performance, and outcome data. The DSMB will make recommendations to the NIDA as to whether there is sufficient support for continuation of the trial, evidence that study procedures should be changed, or evidence that the trial (or a specific site) should be halted for reasons relating to safety of the study participants or inadequate trial performance (e.g., poor recruitment).

Following each DSMB meeting, the NIDA CCTN will communicate the outcomes of the meeting, based on DSMB recommendations, in writing to the study Lead Investigator. This communication detailing study safety information will be submitted to participating IRBs.

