17.1 Primary Outcome Measures

Primary outcome variables for the CHOICES pilot study are:

- 1) HIV provider willingness to prescribe XR-NTX (Aim 1): HIV provider willingness to prescribe opioid antagonist treatment will be assessed with measures adapted from the Medical Opinion Survey (MOS) in the provider survey (mean; survey data).
- 2) Patient acceptance of opioid antagonist therapy (Aim 2): HIV-infected patient acceptance of opioid antagonist treatment will be assessed with measures adapted from the Medical Opinion Survey (MOS), administered during participant recruitment. Patients will be asked whether they are willing to participate in a trial of XR-NTX vs. TAU (binary; survey data).
- 3) Rate of participant recruitment into trial (Aim 3): Number of participants randomized in pilot study per 12 months. This will be used to estimate the speed at which a multisite trial could enroll participants. The number of participants randomized will be assessed on a monthly basis until either 50 participants have enrolled, or 12 months of recruitment have elapsed, whichever comes first (rate; randomization data).
- 4) Treatment initiation (Aim 4A): Treatment initiation is defined as receipt of at least one dose of study medication for those randomized to XR-NTX within 4 weeks of randomization. For those randomized to TAU, treatment initiation will be defined as receiving at least one dose of medication-assisted therapy other than XR-NTX (e.g., buprenorphine for opioid use disorder, disulfiram for alcohol use disorder), or attendance on at least 1 day of non-medication-assisted therapies (e.g., 12-step groups, outpatient rehab referral, etc.) within 4 weeks of randomization. Treatment initiation will be assessed with weekly phone calls from research staff until treatment is initiated or 4 weeks from date of randomization have elapsed, as which point a participant will be considered to have failed treatment initiation. (binary; chart review and self-report).

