17.3 Analysis of Randomized Pilot Study Primary Outcomes

The probability of treatment initiation (Aim 4A) and the probability of retention on treatment (Aim 4B), which are calculated separately for the two arms, are both based on ordinary (conditional) binomial samples, and will be estimated using maximum likelihood techniques, with exact binomial confidence intervals. We do not contemplate a multiplicity adjustment.

The rate of participant recruitment into the trial (Aim 3) can be estimated simply using maximum likelihood assuming an underlying Poisson process, but we feel it is more meaningful and useful for planning to predict the time required for recruitment in a subsequent randomized trial with 400 participants coming from 8 sites. We will do this via a bootstrap simulation. In each iteration of the simulation, the steps will be as follows:

- Draw a bootstrap sample of 8 sites from the 2 pilot-study sites.
- For each site, draw a bootstrap sample of, say, 1000 inter-arrival times from the inter-arrival times for that site to get 1000 simulated enrollment times (starting from time 0) for the site. Note that we consider that the time between the last enrollment at that site and the 12 month time point is also an inter-arrival time for that site. We will use this inter-arrival time in the simulation, but will not associate it with a simulated enrollment¹.
- Treating the 8 bootstrapped sites as simultaneously enrolling, determine T, the time of enrollment of the 400th patient in the simulated trial.

Repeating this iteration 10,000 times will generate 10,000 T-values that will constitute a predictive distribution for the enrollment times in the subsequent randomized trial. It is necessary to assume that the sites in the pilot study are a representative sample of the sites that will participate in the subsequent randomized trial.

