19.0 SAFETY MONITORING

19.1 Data and Safety Monitoring Board (DSMB)

This study will utilize the CTN DSMB to oversee ongoing trial progress to assure protection of participants' safety while maintaining that the study's scientific goals are being met. The CTN DSMB is responsible for conducting periodic reviews of accumulating safety and efficacy data. It will determine whether there is support for continuation of the trial, evidence that study procedures should be changed, or if the trial should be halted (for safety, efficacy, or recruitment or performance reasons). This process is intended to assure the IRBs, sponsor, and investigators that participants are provided with an accurate and ongoing risk evaluation when participating in CTN research trials.

Monitoring will begin with the initial review of the protocol during the study development process and continue throughout the study with meetings at least annually. Recommendations and reports from these reviews will be distributed to the site lead investigator for submission to their IRB.

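### Poor recruitment may halt the pilot or a site although recruitment rate is primary outcome 3, and the section 17.3 forecast would count time after an early closure as failed recruitment

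*Protocol*

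**What the plan says.** Section 17.1 lists as primary outcome 3 "Rate of participant recruitment into trial (Aim 3): Number of participants randomized in pilot study per 12 months", observed "until either 50 participants have enrolled, or 12 months of recruitment have elapsed, whichever comes first". Its purpose is forecasting: "This will be used to estimate the speed at which a multisite trial could enroll participants".

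Section 19.1 makes the DSMB responsible for judging, among other things, "if the trial should be halted (for safety, efficacy, or recruitment or performance reasons". Its reviews "continue throughout the study with meetings at least annually". Section 23.1.3 words this as a recommendation to the sponsor that the trial, or a specific site, be "halted for reasons relating to safety of the study participants or inadequate trial performance (e.g., poor recruitment". Neither section defines poor recruitment or mentions Aim 3.

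Section 17.3 forecasts the time to recruit 400 participants at 8 sites by resampling the 2 pilot sites and their inter-arrival times. For each site, the interval from the last enrollment to month 12 enters as a further waiting time without an enrollment at its end. Nothing is said about a site that stopped recruiting earlier.

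**The concern.** In an efficacy trial slow recruitment is a performance failure. In this pilot it is one possible answer to Objective 3. A halting ground that low values of a primary outcome can trigger would cut short the measurement in the slow scenario that the pilot should be able to detect. A site closed after a slow start stays at its low count and cannot be seen to recover.

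The analysis adds a second problem. If a site is closed at month 6 and its final wait still runs to month 12, six months in which it was not allowed to recruit count as months in which it failed to. The phase III forecast then comes out too long. Early closure also forgoes participants for the estimates of initiation and retention (Aims 4A and 4B).

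**Working it through.** **Inputs from the protocol.** Rates of 1.14 and 2.28 per site-month, 2 pilot sites, limits of 50 participants or 12 months, phase III with 400 participants at 8 sites (sections 17.2 and 17.3); about 25 participants per site in 12 months (section 7.7).

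**Assumptions, not in the protocol.** Poisson arrivals; one review at month 6; a site closes if it then has 6 or fewer participants, which is under half of 25 × 6/12 = 12.5.

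**The plan's own figure.** At 2.28 with 2 sites the expected 12-month count is 2.28 × 2 × 12 = 54.7. Capped at 50, the simulated 20th percentile is 48, as in Table 17.2.1.

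**True phase III times.** 400/(8 × 1.14) = 43.9 months; 400/(8 × 2.28) = 21.9 months.

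**Chance of closure.** Expected count per site at month 6 is 6.84 at the slow rate, so P(6 or fewer) = 0.474. At least one site closes: 1 − (1 − 0.474)² = 0.72. Both close: 0.474² = 0.22. At 2.28, P(6 or fewer) = 0.017, so at least one closes with probability 1 − (1 − 0.017)² = 0.03.

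**How the wording acts.** Suppose one site closes at month 6 with 6 participants and the other recruits at 1.14. The forecast is 50 divided by the mean site rate, because 400/8 = 50.
- Observation ended at closure: site rate 6/6 = 1.00; 50/[(1.00 + 1.14)/2] = 46.7 months.
- Wait run to month 12: site rate 6/12 = 0.50; 50/[(0.50 + 1.14)/2] = 61.0 months.

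**Simulation at 1.14 per site-month** (100,000 pilots; site rate = count/open time):

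| Median forecast, months | Runs with a closure | All runs |
|---|---|---|
| Recruitment continued | 46 | 44.4 |
| Closed, observation ended at closure, mean of site rates | 52 | 48.0 |
| Closed, observation ended at closure, pooled count over site-months | not tabulated | 45.0 |
| Closed, wait run to month 12 as worded | 67 | not tabulated |

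The 90th percentile over all runs goes from 57 to 67 months with observation ended at closure and the mean of site rates.

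**Sensitivity.**
- Closing at 3 or fewer by month 6: closure probability 0.17, overall median unchanged at 44.4, 90th percentile 63 against 57.
- Closing at 6 or fewer by month 9: closure probability 0.22, median 44.4, 90th percentile 60 against 57.
- Whole trial halted at month 6 when below half the count expected at 2.28, true rate 1.14: halt probability about 0.50. The halted-run median is 54.5 months (11 participants: 100 × 6/11), against 50.0 had those runs continued. With the wait run to month 12 it is 109 (100 × 12/11).

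**The section 17.3 bootstrap itself**, slower site always closed at month 6, true value 21.9 months:

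| Site rates | No closure | Ended at closure | Wait to month 12 | Site dropped |
|---|---|---|---|---|
| 2.28 and 2.28 | 21.2 | 22.6 | 28.7 | 20.0 |
| 3.42 and 1.14 | 21.5 | 21.7 | 24.1 | 14.3 |

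**Aims 4A and 4B**, slow rate, first closure rule, all runs: mean sample size falls from about 27 to 21. The exact 95% half-width per arm at p = 0.5 goes from about 0.27 (14 per arm) to about 0.31 (10 per arm).

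**The case against.** The strongest reply is that there is no stopping rule here. The DSMB recommends and the sponsor decides; no trigger is set. Meetings are required only once a year against a recruitment window of at most 12 months, so no review inside the window is assured. Section 19.1 also asks the DSMB to see that the scientific goals are met, and measuring recruitment is one of them. All of this stands: a halt is possible, not built in. A reader might infer that a slow result automatically ends its own measurement; the documents do not support that.

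Two other tempting readings fail as well.
- A reader might infer that closing a site removes randomized participants from Aims 4A and 4B. Section 9.7 keeps participants in follow-up unless they withdraw or are discontinued, and section 17.6 analyzes them as randomized. Only future participants are lost.
- A reader might infer that closure breaks the assumption that begins "It is necessary to assume that the sites in the pilot study are a representative sample of the sites". That assumption concerns which sites are in the pilot, not how long each is observed. A closed site still supplies inter-arrival times. Dropping it would be a threat, but the protocol does not say it would be dropped.

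It can also be said that ending a site's observation at closure is a detail for the statistical analysis plan. That would hold if the protocol were silent, but section 17.3 fixes month 12. Finally, whether a DSMB should keep discretion over a site that enrolls almost nobody is a fair policy question. Table 17.2.1 shows how wide the intervals become at very low yield.

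**Conclusion.** The point holds in a limited form. The protocol names low recruitment as a ground for halting while making recruitment rate a primary outcome with its own fixed end, and section 17.3 would miscount any site closed before month 12.

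The larger distortion comes from the month-12 wording: in runs with a closure, about 67 months against 52 with observation ended at closure and 46 had recruitment continued (true 43.9). Once observation ends at closure the remaining effect is moderate. Over all runs the median moves from 44.4 to between 45 and 48 months depending on the estimator, and with a stricter threshold it does not move, although the upper tail widens. At the planning rate of 2.28 the assumed rule would rarely act (0.03).

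All sizes rest on an assumed review date and threshold and on Poisson arrivals. They show direction and order of magnitude and do not predict what the DSMB would do.

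**What to change.** In sections 19.1 and 23.1.3, state that slow recruitment alone is the Aim 3 result and is not by itself a ground for halting the pilot or a site before 50 participants or 12 months. Keep safety and conduct grounds (data quality, protocol compliance).

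In section 17.3, replace the month-12 end of the final waiting time with the date on which recruitment actually closed at that site, and report any early closure alongside the forecast. The same wording covers a pilot that reaches 50 participants before month 12.

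The cost is wording in three sections. The downside is that a slow site stays open for up to the 12 months already planned, and the DSMB gives up some discretion over a site with very low yield.
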